## **17. Provisions to Monitor the Data to Ensure the Safety of Participants**

We do not believe the research involves more than minimal risk to participants. We will closely monitor all subjects’ responses and record conventional serious adverse events (SAEs) and unexpected and expected adverse events (AEs). For the purposes of study reporting, an SAE is any of the following events: 1. Death within 30 days of CCSH, 2. Suicidal ideation at any time during the study. When any of these events occur, the PI will report these events to the

granting agency (NIH NCCIH). These events will also be reported to the IRB per local reporting requirements

The PI has identified 3 independent scientists who are not related to the study who will serve on the Data and Safety Monitoring Committee (DSMC) for the conduct of this study. Prior to recruitment, the DSMC will review the protocol and monitoring plans. Following this, the DSMC will mainly monitor for adequate recruitment milestones and for the occurrence of adverse events related to participation in the study.

Safety Review Plan Study progress and safety will be reviewed monthly and more frequently if needed. The PI will submit progress reports, including patient recruitment, retention/attrition, and AEs to the DSMC semi-annually. On an annual basis the DSMC will review pertinent aspects of the study to assess subject safety, compliance with the protocol, data collection, and risk-benefit ratio. The PI will generate an Annual Report that will include (1) a list and summary of AEs; (2) whether AE rates are consistent with pre-study assumptions; (3) reason for dropouts from the study; (4) whether all participants met entry criteria; (5) whether continuation of the study is justified on the basis of that additional data are needed to accomplish the aims of the study; and (6) conditions whereby the study might be terminated prematurely. This report will be sent to the DSMC, Emory's IRB, and to the funder (NIH NCCIH).

This study will be stopped prior to its completion if: (1) the intervention is associated with adverse effects that call into question the safety of the intervention; (2) difficulty in study recruitment or retention that will significantly impact the ability to evaluate the study endpoints; (3) any new information becomes available during the trial that necessitates stopping the trial; or (4) other situations occur that might warrant stopping the trial.

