### **13. Risk to Participants**

Hematopoietic stem cell transplant (HSCT) is among the most physically and mentally arduous cancer treatments and patients experience a multitude of acute physical symptoms that negatively impact their QOL and psychosocial well-being. We do not have any reason to believe that CCSH will increase patients' physical, psychological, social, legal, or economic risks. Patients may become upset during the CCSH interventions due to the nature of their treatment, diagnosis, and any emotional discomfort associated with thinking about their disease. However, CCSH has been widely used in usual care in the hospital for 12 months and the chaplains are trained in delivering this type of 'talking therapy'. CCSH is widely associated with low levels of distress.

Risks to confidentiality: The questionnaires that subjects will fill out as part of this study will contain personal information, and participants will have private pieces of audio recorded. We acknowledge that it could be embarrassing if this information were to become public or fall into the hands of someone not associated with the study. We will take the following steps to prevent this from happening: All information obtained from patients will be kept strictly confidential and will be de-identified and stored by a randomly assigned study number, such that these data will be anonymous at all times during data entry and analysis. The key used to link the study number with subject identification will be stored in a password protected, secure database accessible only to study researchers. The key will only be used in the case of study personnel needing to identify a subject and not for data analysis. In addition, all data, including personal identifiers (i.e., name, address, email contact details), will be maintained in secure password-protected electronic files stored on a secure computer system that can only be accessed by study researchers. Emory Spiritual Health supervisors and others in the spiritual health department (other than members of the research team) will not have access to the key nor will they receive any study data.

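### Section 17's two-event list for SAE reporting ignores relatedness, so an unrelated transplant death triggers a report to the funder but another serious event judged related to CCSH does not

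*Protocol*

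**What the plan says.** All of the relevant rules stand in Protocol Section 17.

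- **Recording.** The study will "record conventional serious adverse events (SAEs) and unexpected and expected adverse events (AEs"). This is the broad definition.
- **Definition for reporting.** The next sentence narrows it: "For the purposes of study reporting, an SAE is any of the following events". The list has two items, a death in the 30 days after CCSH and suicidal ideation at whatever point in the study, and no residual category.
- **Trigger.** "When any of these events occur, the PI will report these events to the" granting agency. For the IRB: "These events will also be reported to the IRB per local reporting requirements".
- **Periodic routes.** "The PI will submit progress reports, including patient recruitment, retention/attrition, and AEs to the DSMC semi-annually". An Annual Report listing and summarising AEs goes to the DSMC, the IRB and the funder.
- **Internal review.** Progress and safety are looked at every month, or sooner if required. The text does not say by whom, or who receives the result.
- **Where relatedness matters.** Apart from recruitment, the DSMC's main task is to watch for adverse events related to taking part. Stopping ground (1) is adverse effects associated with the intervention that put its safety in doubt.

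Section 13 names the foreseeable route to harm: "Patients may become upset during the CCSH interventions".

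**The concern.** In transplant inpatients most serious events will come from the disease and the conditioning treatment. A short list for prompt reporting is therefore sensible. What should decide membership of such a list is whether the event may be due to the intervention, and Section 17 does not use that criterion. It includes "Death within 30 days of CCSH" whatever the cause. It leaves out, for example, a serious psychological reaction attributed to a session if suicidal ideation is not expressed.

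The events most informative about harm from CCSH therefore have no stated event-level route to anyone outside the study team, while background deaths have one. The DSMC's remit and stopping ground (1) both turn on related events, so the reporting rule does not serve the decisions it should feed.

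**Working it through.** **1. Follow each kind of event through Section 17.**

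| Event | Recorded | Report to funder when it occurs | Periodic reports |
|---|---|---|---|
| Death within 30 days of CCSH, unrelated | yes | yes | yes |
| Suicidal ideation, any cause | yes | yes | yes |
| Other serious event, judged related to CCSH | yes | none stated | yes |
| Other serious event, unrelated | yes | none stated | yes |

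The last two rows are treated alike. The fourth is a reasonable exclusion; the third is the gap. For the IRB the event-level sentence refers to the same two events but defers to local requirements, which the Protocol does not reproduce, so the gap is firm only for the funder.

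**2. Timing.** Section 7 expects recruitment to take up to 8 months. Section 23 gives November 2021 through July 2022, which is 9 calendar months counted inclusively. If the reporting cycles start with enrolment (an assumption), the first semi-annual report to the DSMC falls at about month 6. The first Annual Report, the only periodic route to the funder and IRB, falls at about month 12, after enrolment has closed.

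**3. Background deaths.** Section 23 cites a transplant trial with 37 deaths before Day 100 among 711 patients.

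- Check of the stated figure: 37/711 = 0.0520, or 5.2%. It reproduces.
- Under an assumed constant hazard, the probability of death by day t is p(t) = 1 − (1 − 37/711)^(t/100).
- The expected number is n × p(t), and the chance of at least one is 1 − (1 − p(t))^n.
- n = 30 and n = 50 are the ends of the range in Section 7.
- The main window is 30 days. As a sensitivity check, a 2–3 week admission plus 30 days gives 14 + 30 = 44 to 21 + 30 = 51 days, in case the window runs from each session through the stay.

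| Window | p(t) | Expected, n = 30 | Expected, n = 50 | At least one, n = 30 | At least one, n = 50 |
|---|---|---|---|---|---|
| 30 days | 1.59% | 0.48 | 0.80 | 38% | 55% |
| 44 days | 2.32% | 0.70 | 1.16 | 51% | 69% |
| 51 days | 2.69% | 0.81 | 1.34 | 56% | 74% |

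A reportable death unrelated to CCSH is thus quite possible.

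**4. Related non-fatal serious events.** The Protocol gives no rate for these, nor for suicidal ideation. Their expected number cannot be derived, and neither can the make-up of the reportable list.

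**The case against.** The best defence is that the narrower definition is expressly limited to study reporting. Recording widely and expediting a short list is a coherent arrangement. That is right: the two definitions do different jobs and do not strictly contradict each other. The weakness lies in how the short list was chosen.

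It can also be said that the stakes are low. Section 17 describes the research as not believed to exceed minimal risk, and Section 13 reports 12 months of use in usual care. Suicidal ideation is listed without a severity or relatedness filter, and becoming upset in a session is not in itself a serious event. This stands, and it limits the importance of the point without removing it.

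A reader might infer several stronger claims that the Protocol does not support.

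- *Related serious events are lost, or lie unseen for up to six months.* They are recorded, and the monthly review could bring one to light and prompt stopping ground (1), which is not tied to any particular report. What is missing is a stated reviewer and a stated route outward from that review.
- *The IRB hears of only two kinds of event.* Local requirements may ask for more, and so may funder terms. Neither is shown.
- *The reportable list will be mainly background deaths.* Without a rate for suicidal ideation this cannot be said; the list may include such deaths.
- *1.6 to 2.6 background deaths should be expected.* Those figures (0.052 × 30 and 0.052 × 50) apply a Day 100 risk to a 30-day window. They are a ceiling for that window.

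**Conclusion.** The point holds as a modest design weakness. Followed as written, Section 17 gives an event-level report to the funder for a death within 30 days whatever its cause, and none for another serious event judged related to CCSH. That fits poorly with the DSMC's remit and with stopping ground (1).

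The textual gap does not depend on any calculation. The size of the background does: about 0.5 to 0.8 expected deaths over 30 days for 30 to 50 patients rests on a constant hazard and on the cited trial's patients being comparable with these autologous recipients. The Protocol establishes neither. The timing argument also assumes that reporting cycles start with enrolment. The number of related events that would go unreported at event level is unknown and, given the minimal-risk description, probably small.

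**What to change.** In Section 17, keep the two listed events and add a third: any other conventional SAE judged at least possibly related to CCSH. State that such an event is reported to the funder and the DSMC when it occurs, and to the IRB under local requirements. Unrelated transplant events stay outside prompt reporting, as they do now.

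The cost is a sentence or so of text and a relatedness judgement for each SAE already being recorded. Few extra reports are expected. The change alters no treatment or clinical rule.

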### **18. Provisions to Protect the Privacy Interest of Participants**

Emory will keep any research records private to the extent that this is required by law. Whenever possible, a study number, rather than your name, will be used on study records. Your name and other identifying information will not appear when we present or publish the study results.

Study records can be opened by court order. They also may be provided in response to a subpoena or a request for the production of documents.

### **19. Economic Burden to Participants**

Study participants will not incur or be responsible for costs because of participation in this research.

### **20. Informed Consent**

**Protocol Title: A feasibility study of Chaplain-delivered compassion meditation for patients receiving stem cell transplantation.**

---

Yes, informed consent will be obtained from both chaplains and patients. Chaplains will be asked to volunteer to participate and will be consented according to standard IRB-approved protocols. To avoid any sense of coercion, all chaplains will be contacted by researchers in private and they will be informed that their participation status will be unknown to all supervisors.

For patients: To avoid any sense of coercion of the potential participant by the patient's physician, an investigator/research assistant will be the recruiter for the study. The physician or nurses may refer a patient who satisfies the inclusion criteria to the recruiter, but he or she will not be the recruiter for the study. All recruited patients engage in a detailed informed consent before the study, prior to becoming a participant.

To minimize burden on the patients and to reduce exposure to study staff, we will conduct informed consent online using a waiver of documented consent.

**Non-English-Speaking Participants**

N/A: all participants will be English-speaking because CCSH is delivered in English.

Participants who are not yet adults (infants, children, teenagers)

N/A: we are not recruiting non-adults

**Cognitively Impaired Adults**

Patient ability to consent will be determined by direct communication between the patient and the study team. Cognitive capacity will be determined if the person is confused, disoriented, unable to make a decision, unable to answer questions, or based on information obtained from family or other caregivers.

**Adults Unable to Consent**

N/A: we will not obtain assent.

**Waiver or Alteration of Consent Process (consent will not be obtained, required information will not be disclosed, or the research involves deception)**

N/A: we will not use a waiver or alteration of the consent process.

**21. HIPAA**

We will not be recording identifiers from the medical record.

## **22. Setting**

The setting will be at Winship Cancer Institute at Emory Hospital.

## **23. Resources Available**

It is expected that enrollment will take place from November 2021 through July 2022.

To recruit patients for this study, we will engage with referring physicians in Emory's Bone Marrow and Stem Cell Transplant Center. We will arrange to give a presentation at the Emory Huddle and/or the center's grand rounds so that providers and staff are familiar with the study.

Lost to follow-up: The funder (NCCIH) considers lost to follow-up as a research subject who was participating in the study at a certain point in time and subsequently missed two consecutive study visits and is unresponsive to study contact or is no longer participating in study activities.

We base our calculations on a large randomized trial of exercise and stress management programs for patients receiving blood and marrow transplant, in which the 120-day lost-to-follow-up was 30.8%. Of 711 consented and randomized, the researchers received final surveys from 492 patients (69.2%): 5 (0.7%) did not undergo HCT, 21 (3.0%) did not receive the intervention, 37 (5.2%) died before Day 100, and 48 (6.8%) died between Day 100 and day 180.

Based on these data, we expect that 97% patients enrolled in the study will complete at least one session of CSH (based on the fact that 3% of patients enrolled in the larger trial withdrew prior to receiving an intervention). Based on the Day 100 completion percentage from that trial (78.8%), we expect that we will have complete data from 78.8% of enrolled patients. However, this is a conservative estimate, given that the 78.8% Day 100 completion rate reported in the previous study is approximately 2.5 month past our final time point for this aim.

